## 8.3 Subject Withdrawal

Subjects may be withdrawn from the study for any of the following reasons:

- Excessive toxicity, prolonged interruption in treatment with study drug, or emergency unblinding due to an adverse event (see section 12)
- Non-compliance with study procedures or reporting
- Non-compliance with study drug dosing
- Withdrawal of consent
- Subjects lost to follow up, with documentation of due diligence
- Any unforeseen event that in the opinion of the treating physician and/or the PI, will prevent the research subject from taking part in this study

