For subjects who are unable to tolerate the protocol-defined dosing schedule, dose adjustments are permitted following guidelines in Table 4 (section 12) in order to keep the subject on study drug. If study drug is interrupted due to toxicity (AE), study drug should not be resumed until recovery to grade  $\leq 1$  is achieved. Depending on AE type and grade, study drug may be re-introduced at the initial dose or a lower dose level (see Table 4). Any changes must be recorded on the appropriate CRF. Additionally, if any surgery is planned, study drug should be interrupted for one week prior to surgery and be re-started as soon as possible following wound healing (default is 2 weeks post-procedure, but may be shortened to 1 week for minor procedures and extended as far as 4 weeks under special circumstances).

Treatment compliance will be monitored via patient diaries and drug accountability procedures. Treatment compliance will be reviewed at each clinical follow-up visit and calculated as the ratio of actual drug taken/expected drug taken. For calculation of treatment compliance, days expected will be corrected to account for days when subject is instructed by study staff to hold medication due to an AE. Subjects unable to provide verification of study dosing compliance via medication diaries and/or drug accountability procedures may be removed from the study due to noncompliance. Likewise, subjects repeatedly with a corrected treatment compliance ratio <75% or >125% despite retraining may also be removed from the study due to noncompliance.

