## 10.3 Study Drug Administration, Compliance and Accountability

Medication will be dispensed to subjects at each visit, with enough supply to cover the visit window time period. Subjects will be instructed on how to prepare and administer study drug in accordance with the protocol. Dispensing of study drug will only be done by designated and qualified individuals at that site location. The study drug is to be taken as a suspension only. For PK/PD analyses, time and dose amount will be captured via CRF when corresponding blood trough levels are obtained (see section 9 above regarding dosing and blood trough level monitoring). An IRB-approved Dosing and Administration instructions for use will be provided to subject families that outlines specific instructions for preparation and use.

If the subject misses a dose (scheduled dose not administered within 12 hours of expected timing), the dose will be skipped. The missed dose will be recorded as not taken in the subjects' medication diary. If the dose is missed/held due an AE, that will be recorded in the subject's medication diary also. Study drug compliance will be assessed by the investigator and/or study team designee at each visit. Parents/LARs will be expected to return both unused and used study drug to the site at each scheduled visit. All doses taken and any adjustments in doses are to be captured on the drug diary CRF.

Subjects who take 75-125% of their drug, excluding days in which they are instructed to temporarily hold study medication by study investigators due to an AE (see section 12), will be considered compliant. Subjects who take <75% or > 125% of their drug, excluding days in which they are instructed to temporarily hold study medication by study investigators due to an AE (see section 12), or subjects for which drug compliance cannot be verified, may be withdrawn from the study (see section 8.3 above).

Upon withdrawal from or completion of the study, any unused study medication is to be returned by the subject.

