## Follow-up Visits

In-person study visits will occur at screening/baseline, Day 7, +1 month following treatment initiation, and then at defined intervals thereafter according to subject's chronological age: 3 months, 6 months, 9 months, and 12 months. Visit schedule windows are +/- 2 weeks from the scheduled visit date, and if the +1 month follow-up visit and the next defined age interval follow-up visits are within 4 weeks of each other, they may be combined into a single in-person study visit. At each visit, a clinical examination with interval medical history that includes concomitant medications and any additional interventional therapies received (including type of intervention and average hours/week of each), safety laboratory studies including sirolimus level, optional biorepository samples, EEG, and study drug accountability will be completed. Seizure diaries and adverse event monitoring and reporting will also be maintained continuously throughout the study and reviewed at each visit. At the in-person follow-up visit at 12 months of age, dMRI, EEG, TAND Checklist, VABS, and Bayley-4 will be performed. To verify durability of treatment effect, at the in-person follow-up visit at 24-months of age, repeat developmental assessment with the addition of the PLS-5 and ADOS-2, accompanied by clinical

examination and an interval medical history that will include any additional treatment interventions, epilepsy history, and therapies, will also be performed.

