## 12.1 Adverse Events, Safety Evaluations, and Reporting

Baseline conditions (e.g. an elevated laboratory value) at study entry will be noted and graded per the CTCAE criteria. For the purposes of this study, an adverse event (AE) is the appearance or worsening of any undesirable sign, symptom, or medical condition occurring after beginning the study drug, whether or not considered drug related. Medical conditions/diseases present before beginning study drug are only considered adverse events if they worsen after starting study drug. Epilepsy and seizures as primary outcome of interest will not be reported as an AE unless accompanied by additional symptoms or events not ordinary in the course of epilepsy management in patients with TSC. Out of range lab results that are considered clinically significant, induce clinical signs or symptoms, or require concomitant intervention or changes in study treatment also will be reported as adverse events.

Following informed consent, all AEs will be captured, graded per the specified parameters, and assigned causality. Adverse events will be assessed in accordance with The Common Toxicity Criteria for Adverse Events (CTCAE v5.0). If the event is not found in the CTCAE criteria, the event will be captured in the "other" category of CTCAE. The occurrence of adverse events should be sought by non-directive questioning of the subject at each visit throughout the study. Adverse events may also be detected when they are volunteered by the subject during or between visits, though physical examination, laboratory tests, or other assessments. Each event should be evaluated to determine:

- 1. Severity grade: CTCAE 1-5
- 2. Relationship to study drug: suspected/not suspected
- 3. Duration: start and end dates (or ongoing at the time of study completion)
- 4. Action taken: no action taken, study drug dosage adjusted/interrupted, study drug permanently discontinued, concomitant medication taken, non-drug therapy given, hospitalization/prolonged hospitalization

5. Whether it is a serious adverse event (SAE) as defined by the FDA and described below in section 12.2.

All adverse events should be treated appropriately. If any concomitant medication or non-drug therapy is given as a result, these should be recorded on the appropriate CRF.

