Once an adverse event is detected, it should be followed until resolution, with an assessment made at each study visit to make note of any changes in severity, suspected relationship to study drug, interventions require, and the outcome. In addition, all adverse events will be recorded and subjects will be followed for 30 days after the last dose of study drug. At the end of the 30-day period, the Principal Investigator will determine if the patient is stable and the tracking of ongoing AE's can be discontinued. New AEs will not be captured beyond the 30-day period. At the end of the 30-day period, AEs that have not resolved (e.g. returned to at least baseline) will be documented as ongoing.

Periodic summary reports of AEs will be provided to the independent medical monitor, DSMB, and Tavanta Therapeutics, Inc. —the supplier for TAVT-18 for this study. Patient confidentiality will be maintained at all times. No PHI will be included in AE summary reports.

All adverse events are to be reported as follows, unless they meet the definition of a Serious Adverse Event described in section 12.2:

- FDA Reporting: Annually
- DSMB: Per DSMB Charter
- IRB: Per IRB requirements
- Study sponsor, independent medical monitor, and drug supplier: Monthly

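### Sections 8.3, 9.1 and 10.3 permit removing an infant from the study, not only from drug, for toxicity, interruption or dosing non-compliance, and no stated rule keeps a removed infant in seizure follow-up

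*Combined protocol and SAP*

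**What the plan says.** Section 8.3 opens with "Subjects may be withdrawn from the study for any of the following reasons". The list includes "Excessive toxicity, prolonged interruption in treatment with study drug, or emergency unblinding due to an adverse event (see section 12") and "Non-compliance with study drug dosing". The unblinding clause is left over from the deleted randomized stage and plays no part here.

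Two other sections point the same way for compliance outside 75% to 125%:
- Section 9.1: infants repeatedly outside the range "despite retraining may also be removed from the study due to noncompliance".
- Section 10.3: such infants, or those whose compliance cannot be verified, "may be withdrawn from the study (see section 8.3 above").

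Elsewhere the protocol treats stopping drug as a separate act. Section 12.1 lists "study drug permanently discontinued" among the actions taken for an adverse event, and Table 4 speaks of discontinuing study drug. The visit schedule in section 11.5 is not tied to dosing: after the 1-month visit, visits occur "then at defined intervals thereafter according to subject's chronological age", at 3, 6, 9 and 12 months.

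For the period after stopping, section 12.1 says that "subjects will be followed for 30 days after the last dose of study drug". Sections 12.2 and 13 use the same 30 days for serious events and concomitant medication.

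**The concern.** Toxicity, prolonged interruption and poor dosing compliance are events of treatment, yet the consequence allowed for each is exit from the study. Efficacy is one of the two primary endpoints (section 4.1). Section 16.1 plans to compare age at seizure onset, 12-month seizure frequency and infantile spasms with 32 historical controls.

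If infants leave because they tolerate the drug poorly or receive little of it, the missing data are related to tolerability and exposure. Censoring them at exit may then be informative, and the direction of any bias is unknown. A survival analysis can use follow-up up to exit, but it cannot supply the 12-month outcomes of an infant who is no longer seen.

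The primary safety endpoint is little affected, because the event that leads to exit has already been recorded. What is at stake is the quality of the descriptive efficacy data, which section 16.2 wants for estimating effect size and variability in any later trial.

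**Working it through.** The plan has no figure of its own to reproduce here: section 16.2 states that the study is no longer powered, and n=5 is set by design. The check is a reading of the text, followed by simple bounds.

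**Does any text keep a removed infant in follow-up?**
- Section 11.5: visits run by age, and phone visits with diary review occur at least monthly for the whole study. This covers infants still in the study and does not mention those withdrawn.
- Table 3 footnote 1 and section 11.6 (Laboratory Evaluations): an infant recently off drug at a visit misses only the sirolimus level. So being off drug is foreseen and does not end participation. Withdrawn infants are again not mentioned.
- Section 9.2: a first seizure does not require stopping drug. This does not address the grounds in section 8.3.
- Section 11.5 (Post-treatment follow-up): enrolled subjects have a 24-month developmental assessment and epilepsy history, and may be contacted yearly. Whether this applies after withdrawal is not stated, and it does not replace the 12-month visit.
- Section 11.6: outside clinical records and clinical EEGs may be collected. These could recover some onset dates.
- Sections 12.1, 12.2 and 13: the 30 days are windows for adverse events and concomitant medication. They neither end nor extend seizure follow-up.

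The gap therefore exists only for infants actually removed under section 8.3.

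**How much could removal matter?**

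Inputs: n = 5 treated (section 16.2); 90% Wilson-type intervals are the plan's choice for safety percentages (section 16.1) and are borrowed here for scale. Assumptions: w infants are removed before 12 months with no seizure so far and their later status is unknown; s of the remaining 5 − w have seizures.

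Observed proportion = s/(5 − w). The full-cohort proportion lies between s/5 and (s + w)/5.

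- w = 1, s = 1: observed 1/4 = 25%; range 1/5 to 2/5 = 20% to 40%.
- w = 2, s = 1: observed 1/3 = 33%; range 1/5 to 3/5 = 20% to 60%.

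For comparison, the 90% Wilson interval for 1/5 with nobody lost, with z = 1.645 and z² = 2.706:
- Centre = (0.2 + 2.706/10) / (1 + 2.706/5) = 0.4706/1.5411 = 0.305.
- Half-width = 1.645 × √(0.2 × 0.8/5 + 2.706/100) / 1.5411 = 0.259.
- Limits, before rounding the parts: 0.046 to 0.565, or 5% to 56%.

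The ranges from loss lie largely inside this interval. They measure something different, namely missing outcomes and not sampling error, and come on top of it.

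**The case against.** The strongest reply is that section 8.3 grants a permission and imposes no duty, and that the rest of the protocol leans towards keeping infants in view. Visits follow age, monthly calls continue, and Table 4 speaks only of drug. The 24-month history, yearly contact and clinical records might recover onset age. The consent form was not available to me and may say more. The study is a pilot of five infants whose core is a 14-day pharmacokinetic phase, and its sampling uncertainty is already very wide.

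Most of this stands, and it limits the point. It does not remove it: none of these provisions says what happens to an infant withdrawn on the three grounds, and none secures the 12-month assessment.

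Three stronger readings are tempting but unsupported:
- That follow-up ends 30 days after the last dose. It does not; those 30 days concern adverse events and concomitant medication, and the age-based schedule continues for an infant who has only stopped drug.
- That a removal rate can be taken from section 3, where 23% of infants stopped everolimus for adverse events. That figure is retrospective, concerns another drug, and counts stopping drug, not leaving a study. The documents give no removal rate for this trial.
- That removed infants are dropped from the analysis because section 8 counts as evaluable only those with the 12-month assessment. Section 16 does not use that definition, and section 16.1 reads as covering all treated infants.

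**Conclusion.** The point holds in a limited form. Three treatment-related grounds permit removal from the study itself, and no stated rule keeps an infant so removed in seizure follow-up or the 12-month assessment. If the permission is used, efficacy data may be lost selectively; one loss can leave the seizure proportion anywhere from 20% to 40%, and two losses from 20% to 60%, in the examples shown. These figures assume that the removed infants' later status is not recovered from clinical records or the 24-month history. How often removal would occur is unknown.

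No confirmatory conclusion depends on this. It is a cheap improvement that the sponsor should consider, not a flaw that invalidates the design.

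**What to change.** - In sections 8.3, 9.1 and 10.3, make excessive toxicity, prolonged interruption and dosing non-compliance reasons to stop study drug only. The other grounds, such as withdrawal of consent and loss to follow-up, can remain study exits.
- While the family consents, continue the scheduled seizure diary, EEG and 12- and 24-month assessments. Do research dMRI only alongside a clinical MRI, so that no infant is sedated for research alone.
- State that the bans on prophylactic vigabatrin (section 9.2) and on other mTOR inhibitors (section 13) end when study drug is permanently stopped, so that staying in follow-up does not restrict care.
- Record the stop date and any later anti-seizure or mTOR treatment.
- State that the seizure-onset analysis in section 16.1 includes all treated infants.

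The cost is a short protocol and consent amendment, plus a few visits already in the schedule for any infant who stops early. Table 3 footnote 3 says the EEG schedule matches clinical guidelines. The drawbacks are real: time off drug dilutes any apparent effect, later treatment may confound it, and some families may decline.

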## 9 STUDY TREATMENT AND DOSING

## 9.1 STUDY MEDICATION (TAVT-18 SIROLIMUS)

The half-life of sirolimus (TAVT-18) is estimated to be >30 hours, allowing for convenient twice daily oral dosing. Medication should be taken in the fed state, defined as within 30 minutes of feeding. An individualized PK model-informed age-adjusted dosing scheme with a starting dose based on age at the time of enrollment (see Table 2) will be utilized, which is based on previous experience and simulation analysis of data obtained from our previous studies treating infants with congenital vascular anomalies with RapamuneTM 49, 77, 82 and preclinical and human studies with TAVT-18. These targeted doses are estimated based on the assumption that the oral bioavailability of TAVT-18 is 2-times higher compared to RapamuneTM. The target pre-dose whole blood trough sirolimus concentration (Cmin) will be 10 ng/mL with an upper tolerance range of 10-15 ng/mL. This target is consistent with prior published experience from infants treated with sirolimus for clinical indications and previous clinical trials in TSC patients treated for SEGA or epilepsy.

Table 2: Estimated	l sirolimus (TAVT-18) starting doses for the indicated target
concentration rang	ge 
Age group	Dosing for target concentration range = 10-15 ng/ml

(months)	
0-1	$0.2 \text{ mg/m}^2/\text{dose}$ , administered twice daily (total daily dose = $0.4 \text{ mg/m}^2$ )
1-2	$0.25 \text{ mg/m}^2/\text{dose}$ , administered twice daily (total daily dose = $0.5 \text{ mg/m}^2$ )
2-3	$0.3 \text{ mg/m}^2/\text{dose}$ , administered twice daily (total daily dose = $0.6 \text{ mg/m}^2$ )
3-4	$0.35 \text{ mg/m}^2/\text{dose}$ , administered twice daily (total daily dose = $0.7 \text{ mg/m}^2$ )

4-6	$0.45 \text{ mg/m}^2/\text{dose}$ , administered twice daily (total daily dose = 0.9 mg/m 	5

Steady state whole blood trough levels should be drawn in the morning, approximately 24-hours since last dose of study medication, after the subject has been on continued dosing for 7-14 days. Sirolimus trough level may be drawn at the participating study center or drawn locally and sent to the reference laboratory, whichever is easier for the subject. Subjects for which treatment is held temporarily due to an AE but resumed at same dosing as prior to the AE (see section 12) do not require a repeat sirolimus whole blood trough level to be checked when resuming treatment after the AE has resolved.

Whole blood sirolimus trough levels will be assessed at defined intervals after the initial dose (+1, +3, +6, +24 hours). Infants will continue daily dosing at the same dose, orally twice/daily within 30 minutes of feeding, for an additional 6 days  $(\pm 1 \text{ day})$ , when the steady state sirolimus whole blood trough levels will be assessed at defined intervals of +1, and +3 hours post-dose. Based on resultant steady-state measured trough level at day 7, sirolimus dosing will be adjusted per protocol (see next paragraph) to achieve the desired precision dosing target of 10 ng/ml. Treatment at the adjusted dosing will continue an additional 6 days  $(\pm 1 \text{ day})$ , after which the steady state sirolimus trough level will be measured again (day 14). Subject recruitment and participation is an essential component to the success of the overall study, but it is recognized enrollment is unlikely unless given opportunity to continue treatment beyond 14 days given the potential for direct benefit (see section 6.2 above) provided no individual- or group-level safety concerns are encountered. Accordingly, after the day 14 sirolimus trough level, participants can elect to continue open-label treatment with TAVT-18 (sirolimus) up to 12-months of age, providing additional extended exposure dosing and safety data for TAVT-18. For additional details, see section 11.2 below.

During open-label treatment with TAVT-18 (sirolimus), participants will have already had their first steady sirolimus whole blood trough concentration measured at 7 and 14 days after initiating treatment and subsequent dosing will be individually adjusted using real-time drug concentration measurements in combination with a Bayesian population model-based target optimization approach. Sirolimus trough levels also will be obtained in conjunction with safety labs (CBC with differential, comprehensive metabolic panel, lipid profile, amylase, and lipase) drawn at each clinical follow-up visit (1, 3, 6, 9, and 12 months). Patients will keep a diary of dosing information recording exact dosing times, time of last feeding, and dosing amount administered. Any missed doses will be reviewed at each visit to document adherence. Sirolimus concentrations will be determined at the CLIA-certified laboratory located at Cincinnati Children's using a validated tandem mass spectrometry assay performed using electrospray on a Waters Quattro Micro API triple quadrupole mass spectrometer interfaced with an Acquity Ultra Performance Liquid Chromatography instrument (Water Corporation, Milford, MA). The dynamic range of the assay is 0.5–100.0 ng/mL. As we did previously, a central physician not involved in patient care or study assessments will monitor sirolimus results and provide protocolspecified dosing adjustments in real time Patients may continue treatment clinically (nonresearch) with sirolimus after the 12-month follow-up visit if clinically indicated. However, research study medication will not be provided beyond the final follow-up visit, so sirolimus must be sourced through normal clinical supply channels in such instances.

For subjects who are unable to tolerate the protocol-defined dosing schedule, dose adjustments are permitted following guidelines in Table 4 (section 12) in order to keep the subject on study drug. If study drug is interrupted due to toxicity (AE), study drug should not be resumed until recovery to grade  $\leq 1$  is achieved. Depending on AE type and grade, study drug may be re-introduced at the initial dose or a lower dose level (see Table 4). Any changes must be recorded on the appropriate CRF. Additionally, if any surgery is planned, study drug should be interrupted for one week prior to surgery and be re-started as soon as possible following wound healing (default is 2 weeks post-procedure, but may be shortened to 1 week for minor procedures and extended as far as 4 weeks under special circumstances).

Treatment compliance will be monitored via patient diaries and drug accountability procedures. Treatment compliance will be reviewed at each clinical follow-up visit and calculated as the ratio of actual drug taken/expected drug taken. For calculation of treatment compliance, days expected will be corrected to account for days when subject is instructed by study staff to hold medication due to an AE. Subjects unable to provide verification of study dosing compliance via medication diaries and/or drug accountability procedures may be removed from the study due to noncompliance. Likewise, subjects repeatedly with a corrected treatment compliance ratio <75% or >125% despite retraining may also be removed from the study due to noncompliance.

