#### **TABLE 3: Schedule of Study Procedures/Events**

Neuropsych assessment 						Х	Х
Dispense Study Drug	Х	Х	Х	Х	Х		
Interim phone vists 							

Subjects may be enrolled into the study at any time between the ages of 0-6 months and will receive TAVT-18 (sirolimus) until 12 months of age. Visit window for follow-up visits is  $\pm 2$  weeks.

Includes option for additional bloodwork for exploratory measures; subjects not taking study medication within the previous 48 hours of the study visit due to AE or other reasons will not have sirolimus level assessed.

Sirolimus trough levels should be drawn in the morning, approx. 24hrs after last dose of study medication. The initial level will be drawn 7-14 days after subject has been on steady dosing and in conjunction with safety labs at each clinic follow-up visit (1,3,6,9,12 mths). Similarly, trough levels will be drawn at 7-14 days after any dose modification, until target concentration is reached. For convenience, levels can be drawn at the study center or drawn locally and sent to the reference laboratory.

Routine EEG (60 minutes duration). EEG acquisition schedule for study is consistent with current TSC clinical guideline recommendations dMRI is 15-minute add-on sequence to conventional MRI that is recommended clinically every 1-3 years in TSC.

Developmental assessment consists of TAND Checklist, VABS, and Bayley-4 at the 12 months of Age visit and TAND Checklist, VABS, Bayley-4, PLS-5, and ADOS-2 at the 24 months of Age visit

Monthly calls will occur in between in-person visits. During the first month in the study, phone calls will occur weekly.

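### Steady-state troughs are ordered about 24 h after the last dose, which does not fit twice-daily dosing to a pre-dose target

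*Combined protocol and SAP*

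**What the plan says.** Section 9.1 justifies the regimen by a half-life above 30 h, "allowing for convenient twice daily oral dosing", and every row of Table 2 is twice daily. The dosing target is defined at a specific moment: "The target pre-dose whole blood trough sirolimus concentration" (C_min) "will be 10 ng/mL with an upper tolerance range of 10-15 ng/mL".

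The same section then sets the sampling rule: "Steady state whole blood trough levels should be drawn in the morning, approximately 24-hours since last dose of study medication", once the infant has had 7–14 days of continued dosing. Table 3 footnote 2 repeats it as "approx. 24hrs after last dose of study medication".

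For day 7, section 9.1 describes the visit as the point "when the steady state sirolimus whole blood trough levels will be assessed at defined intervals of +1, and +3 hours post-dose", and section 11.2 gives the same two times. The next step is a dose change: "Based on resultant steady-state measured trough level at day 7, sirolimus dosing will be adjusted per protocol (see next paragraph"). The paragraph it points to describes individual adjustment with a Bayesian population model and says that steady-state troughs are measured at 7 and 14 days. Dose times are recorded in the family diary (9.1) and on the CRF at each blood draw (10.3, 11.6).

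**The concern.** On a 12-hourly schedule, the level just before the morning dose is about 12 h after the last dose. A sample 24 h after the last dose exists only if the evening dose was left out. A family that doses as told therefore cannot satisfy the sampling rule, and a family that skips a dose to satisfy it produces a level that is not the targeted quantity. Levels may be drawn locally, so staff outside the study centre may be working from the written rule.

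A level drawn at 24 h but read as the pre-dose C_min is too low and pushes the dose up, in infants who start treatment at 0–6 months. Dose verification is also the main product of this five-infant study. Questions 1 and 2 to the DSMB (section 11.3) ask whether the starting doses reach 5–15 ng/mL and whether the precision-dosing strategy reaches a trough of 10 ng/mL. Both answers depend on what the word trough means.

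The day-7 text adds a labelling problem. It calls +1 and +3 h samples troughs, lists no explicit pre-dose sample, and then changes the dose on a measured trough.

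**Working it through.** The plan gives no figure to reproduce here, so the check compares the instructions and then estimates the size of the mismatch.

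**Inputs from the protocol.** Dosing interval 12 h (9.1, Table 2); half-life above 30 h (9.1); target 10 ng/mL with upper tolerance 10–15 (9.1); trough draw at about 24 h (9.1, Table 3 footnote 2); adult mean t_max under 1 h (10.1).

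**Assumptions.** One compartment, with absorption complete well before 12 h. Half-life 30–60 h, with 90 h as a sensitivity value, because the protocol gives only a lower bound. That bound cites a healthy-volunteer study. No infant half-life is given, and a shorter one would widen the gap.

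**Step 1: 24-h level relative to the 12-h pre-dose level at steady state.** C24/C12 = 2^(−12/half-life).
- 30 h: 2^(−0.400) = 0.758, so 24% low
- 60 h: 2^(−0.200) = 0.871, so 13% low
- 90 h: 2^(−0.133) = 0.912, so 9% low

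**Step 2: pre-dose level if the 24-h reading is titrated to 10.** 10 ÷ (C24/C12).
- 30 h: 10/0.758 = 13.2 ng/mL
- 60 h: 10/0.871 = 11.5 ng/mL
- 90 h: 10/0.912 = 11.0 ng/mL

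**Step 3: 24-h reading at which the pre-dose level equals 15.** 15 × (C24/C12).
- 30 h: 15 × 0.758 = 11.4 ng/mL
- 60 h: 15 × 0.871 = 13.1 ng/mL
- 90 h: 15 × 0.912 = 13.7 ng/mL

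Readings between these values and 15 look acceptable but correspond to a pre-dose level above the tolerance limit.

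**Step 4: can a size be put on the day-7 ambiguity?** Only loosely, because steady state is not assured by day 7. The fraction reached after 144 h of dosing is 1 − 2^(−144/half-life): 96% at 30 h, 81% at 60 h, 67% at 90 h.

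To allow for this, sum the single-dose curves ka/(ka − k) × [exp(−kt) − exp(−ka·t)] over 12-hourly doses from hour 0, where k = ln 2/half-life and ka is assumed to be 2–5 per hour. Compare a +1 or +3 h sample after the hour-144 dose with a 24-h sample at hour 312, on an unchanged dose:
- 30 h: day 7 reads 58–65% higher
- 60 h: day 7 reads 10–12% higher
- 90 h: day 7 reads 7–9% lower

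If a +1 or +3 h reading on day 7 were itself titrated to 10, the eventual pre-dose level would be about 8.0–8.4 ng/mL at 30 h but 10.6–10.8 at 60 h. Neither the size nor the sign of a day-7 effect is fixed.

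**The case against.** The strongest reply is that the plan does not dose by comparing a raw reading with 10. Section 9.1 uses a Bayesian population model, DSMB question 2 names a model-based strategy, and section 16.1 models concentrations by sampling time. With recorded dose and draw times, such a model can use a sample taken at any hour. In addition, the 24-h result stays within 10–15 when titrated to 10, levels are repeated 7–14 days after each dose change, and one central physician reviews the results in a single-site pilot.

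Much of this stands, and it makes the figures upper bounds. But section 9.1 does not say that actual sampling times enter the model, it ties the day-7 change to a measured trough, and no model tells a family whether to give the evening dose.

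A reader might also infer more than the text supports:
- **That +1 or +3 h values are used as C_min on day 7.** Nothing says so. Section 9.1 uses the word trough just as loosely for the day-1 samples, and a trough plus two post-dose samples is a natural reading.
- **That day 14 has no sampling time.** The general rule in 9.1 and footnote 2 covers the draws at 7–14 days.
- **That the 48-hour condition in section 11.6 relaxes the timing.** It decides only whether a level is measured at all, in line with Table 3 footnote 1.
- **That day 7 reads higher than day 14 by a known amount.** Step 4 shows that the sign can reverse.

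**Conclusion.** The 24-h rule is wrong as written, in two operative places, and should be corrected. It conflicts with twice-daily dosing and with a target defined before the dose.

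At face value it understates the pre-dose level by about 13–24%. This assumes one compartment, steady state, a half-life of 30–60 h and no model correction for sampling time. The consequence is upward dose pressure of moderate size: 11.5–13.2 ng/mL when aiming for 10, with levels above 15 hidden once the reading passes 11.4–13.1. The documents do not show that infants would be overdosed, since the model may absorb part or all of the error.

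The day-7 wording is a lesser defect: ambiguous labelling and no explicit pre-dose sample, with no defensible single figure for its effect.

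**What to change.** In section 9.1 and Table 3 footnote 2, define the trough as the sample taken immediately before the morning dose, about 12 h after the previous dose. In 9.1 and 11.2, list a pre-dose sample on day 7 and on day 14, and base the day-7 adjustment on the day-7 pre-dose sample. Relabel the +1, +3 and +6 h samples as post-dose concentrations. State in 9.1 that actual dose and draw times enter the Bayesian model.

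The cost is amendment wording and at most one small extra blood sample on day 7, when a PK visit is already scheduled.

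The same amendment could settle a separate clerical point: section 11.2 requires safety labs on days 7 and 14, which Table 3 and the laboratory list in 11.6 omit.
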